### **9.2. Dose Delays and Dose Modifications for Toxicity**

*For any given subject, study drug infusions should not begin if the subject's mean arterial pressure (MAP) is less than 65 mmHg.*

For any given subject, hold blinded GC4419/placebo and reduce by 25% (from the initial dose) for all future infusions if:

- During infusion or within 1 hour of completing infusion, the subject experiences an acute decrease in systolic blood pressure requiring bolus fluid resuscitation OR requiring initiation of vasopressor therapy OR increased vasopressor therapy. Hold GC4419/placebo until the dose of vasopressor therapy is stable and bolus fluid resuscitation is not required.
- The subject develops serum creatinine  $> 5$  mg/dL. Hold GC4419/placebo until the creatinine is  $=< 5$  mg/dL.
- The subject develops serum total bilirubin  $> 6$  mg/dL, or AST or ALT  $> 10$  times upper limit of normal. Hold GC4419/placebo until the parameters in question are below these levels.
- The subject experiences a serious or severe adverse event considered by the investigator to be related or possibly related to blinded GC4419/placebo. Hold GC4419/placebo until the event is no longer serious or severe.

Up to two such dose reductions for a cumulative 50% from the initial dose of GC4419/placebo will be permitted for a given subject. If a subject cannot tolerate GC4419/placebo infusion after a 50% dose reduction, all dosing with GC4419/placebo for that subject will be discontinued.

Patients unable to tolerate GC4419/placebo must discontinue treatment with GC4419/placebo but should continue with other protocol assessments at the discretion of the treating investigator and with the ongoing consent of the subject.

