### **10.5.3. Clinical Laboratory Abnormalities and Other Abnormal Assessments as AEs and SAEs**

Clinically significant abnormal laboratory findings or other abnormal assessments that are associated with the disease being studied, unless judged by the investigator as more severe than expected for the patient's condition, or that are present or detected at the time of the baseline visit and do not worsen, will not be reported as AEs or SAEs.

A laboratory abnormality reported by the local laboratory may meet the criteria to qualify as an AE or SAE as described in this protocol. Laboratory abnormalities should only be recorded in the AE section of the CRF if at least one of the following criteria is met:

- Meets the criteria of an SAE

- Treatment is initiated specifically for the abnormality
- Investigational product was discontinued
- Grade 3 or Grade 4 abnormalities not present at baseline, and more severe than expected for the patient's condition in the judgment of the treating investigator

For laboratory abnormalities meeting the criteria of SAEs, the site must complete and send the SAE report including the laboratory report (as regionally required) to the sponsor using the SAE form.

Abnormal assessments (eg, ECGs) that are judged by the investigator as clinically significant will be recorded as AEs or SAEs if they meet the definitions as defined in [Section 10.4](#).

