## 10.7. Recording Adverse Events

All AEs must be recorded on the appropriate CRF regardless of the severity or relationship to GC4419/placebo. All AEs that meet the seriousness criteria should also be recorded on the SAE Report Form. All SAEs must be reported to the Sponsor or delegated organization within the timeline stated in [Section 10.5](#).

The recording of AEs will be based on data obtained from the following sources:

- Medical and surgical history
- Physical examinations including vital signs
- Clinical laboratory test results
- Subject verbal reports to the investigational staff and documented in the medical chart

All clinical events, including both observed (such as any reaction at sites of application) and volunteered problems, complaints, or symptoms, are to be recorded. The need to capture this information is not dependent upon whether the clinical event is associated with GC4419/placebo use. AEs resulting from concurrent illnesses, reactions to concurrent medications are also to be recorded.

The information to be recorded for AEs will include:

- The specific type of event in standard medical terminology – diagnosis if known, is preferred over symptoms
- Duration of the clinical event (start and stop dates)
- Severity (Grade 1, 2, 3, 4, or 5) of the clinical event
- Seriousness (SAE) criteria, if applicable
- Relationship of the AE to GC4419/placebo as defined in [Section 10.6](#)
- Management of GC4419/placebo administration and other action taken to alleviate the clinical events

- Clinical outcome of the AE

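### Section 10.5.3 records a laboratory abnormality as an AE when drug is discontinued but not when it is held or reduced, so a value that changes dosing under Section 9.2 could be absent from the AE tables

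*Combined protocol and SAP*

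**What the plan says.** Section 10.5.3 sets an exclusive condition: "Laboratory abnormalities should only be recorded in the AE section of the CRF if at least one of the following criteria is met". Four criteria follow:

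- "Meets the criteria of an SAE"
- "Treatment is initiated specifically for the abnormality"
- "Investigational product was discontinued"
- a Grade 3 or 4 abnormality that is "not present at baseline, and more severe than expected for the patient's condition in the judgment of the treating investigator"

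The paragraph before the list also removes clinically significant findings that belong to the disease under study, unless the investigator considers them worse than expected for that patient.

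Section 9.2 (repeated in the Synopsis) instructs sites to "hold blinded GC4419/placebo and reduce by 25% (from the initial dose) for all future infusions if" any of four triggers occurs. Two of the four are purely laboratory values: creatinine above 5 mg/dL, and total bilirubin above 6 mg/dL or AST or ALT above 10 times ULN. For the liver trigger the instruction is "Hold GC4419/placebo until the parameters in question are below these levels". Up to two reductions are allowed. Discontinuation is a later, separate step, for a subject who cannot tolerate the infusion after a 50% reduction.

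Section 10.7 lists what is collected for each AE, including "Management of GC4419/placebo administration and other action taken to alleviate the clinical events". Section 11.6 tabulates recorded AEs by subject and, separately, summarizes laboratory measurements by treatment group at the scheduled time points.

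**The concern.** The same laboratory value can be a toxicity in Section 9.2, serious enough to change every later infusion, and no event at all in Section 10.5.3. The only criterion there about action on study drug is discontinuation, which is not what Section 9.2 requires at the laboratory thresholds. The grade criterion depends on what the investigator considers expected, and Section 4.1.1 lists renal and hepatic damage among the comorbidities of critical COVID-19. Expected is therefore a ready answer for these two organs.

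At stake is how the AE tables read. The Synopsis describes the trial as an initial assessment of safety in critically ill patients, and Section 4.2 reports no apparent nephrotoxicity or hepatotoxicity so far, with studies in renal and hepatic impairment still in progress. If a dose-changing creatinine or transaminase value has no AE entry, the study-drug management field in Section 10.7 has nothing to attach to, and the AE tables cannot explain the dose reduction.

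**Working it through.** The plan gives no figure on this point, so the check sets the two rules side by side.

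**1. The recording rule (Section 10.5.3).** A laboratory abnormality is recorded if S or T or D or G, where S = meets SAE criteria, T = treatment started for it, D = investigational product discontinued, and G = Grade 3 or 4 *and* not present at baseline *and* judged more severe than expected.

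**2. The four Section 9.2 triggers against that rule.**

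| Trigger in 9.2 | Subject to the four criteria? |
|---|---|
| Blood pressure fall needing fluid bolus or vasopressor change | No, not a laboratory value |
| Creatinine > 5 mg/dL | Yes |
| Bilirubin > 6 mg/dL, or AST/ALT > 10 x ULN | Yes |
| Related serious or severe AE | No, already an AE |

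**3. The case that escapes.** A threshold is crossed; drug is held, then resumed at a reduced dose. Section 9.2 uses hold, reduce and discontinue as different steps, so D = no. Suppose the event is not an SAE (S = no), nothing is started specifically for it (T = no), and the investigator regards it as expected. Then G = no whatever the grade, and none of the four criteria is met. Because Section 9.2 allows two reductions (100% to 75% to 50% of the initial dose) before discontinuation comes into play, this can happen twice in one subject with D still unmet.

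**4. The opening paragraph.** Even if the third criterion covered holds and reductions, the exclusion of disease-associated findings would still apply on the same judgement. Both parts of Section 10.5.3 conflict with Section 9.2.

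**5. Other routes into the AE tables.** Section 10.5.2 counts adverse medical conditions that begin on or after the baseline visit as AEs, and Section 10.7 prefers a diagnosis, if known, to symptoms. If the investigator diagnoses kidney or liver injury behind the value, that condition can be recorded outside the laboratory list. Absence from the AE tables therefore also requires that no such diagnosis is entered.

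**6. What remains outside the AE tables.** Laboratory values are summarized by arm (Section 11.6), the worst value is kept on days with several draws (Appendix 1, footnote 9), and infusion volumes and start and stop times go on the CRF (Section 8.3.6). Crossings and holds could be rebuilt from these. The time-point summaries do not themselves count crossings or tie them to a dose change.

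**7. Effect on a table.** Let d be the difference between arms in the proportion of subjects with such an event, and f the fraction of those subjects with no AE entry, the same in both arms because the judgement is made blinded. The AE table then shows on average (1 - f) x d. With 25 per arm, one subject is 1/25 = 4 percentage points. The documents give neither d nor f; f could lie anywhere from 0 (all recorded) to 1 (none recorded).

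**The case against.** The strongest reply is that the escaping case needs several conditions together: not serious (and seriousness includes prolonged hospitalization and other important medical events, Section 10.4.2), not treated, drug not discontinued, judged expected, and not entered as a diagnosis. Entry requires AST and ALT at or below 2.5 times ULN, so a transaminase hold means at least a 10 / 2.5 = fourfold rise above the entry ceiling, which many investigators would call unexpected or diagnose. The gravest renal cases are likely to be caught by treatment, or by the Synopsis rule that stops dosing when continuous renal replacement therapy exceeds 24 hours. This stands: the gap is conditional, and nothing in the documents shows that the escaping case is usual.

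It is also fair that the Data Monitoring Committee reviews unblinded safety data and other clinical data it finds relevant (Section 14.4), that Sections 11.1 and 11.6 defer detail to a separate statistical analysis plan that may include a table of holds and reductions, and that limiting laboratory AEs in a critically ill population is a deliberate way to contain noise. The first two mean that the lack of such a table in Section 11.6 is not itself an error. The third supports filtering in general, but not filtering out values that the protocol itself treats as toxicity.

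A reader might infer that renal and hepatic toxicity would be under-counted, that the signal is lost, or that one arm is favoured. The documents support none of these. The diagnosis route exists, the underlying data are kept, and the judgement is blinded.

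**Conclusion.** The gap in the wording is real: a stated rule, not a missing detail, could leave a dose-changing laboratory value out of the Section 11.6 AE tables. It bites only when the value is judged expected, non-serious and untreated, and is not recorded as a diagnosed condition. The loss is confined to the AE tables and to the recorded link between the abnormality and the dose change. No size of under-count can be given from the documents.

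The conclusion rests on two readings: that discontinued in Section 10.5.3 does not include a temporary hold, which the distinct terms in Section 9.2 support; and that the specific condition in Section 10.5.3 governs laboratory values ahead of the general instruction in Section 10.5.2 to record all AEs. No view is taken on the hold or reduction thresholds.

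**What to change.** In Section 10.5.3, change the third criterion to *Investigational product was held, reduced or discontinued*. Add one sentence saying that a laboratory value triggering a Section 9.2 hold is recorded as an AE notwithstanding the disease-associated exclusion in the opening paragraph. The second step is needed because the first alone leaves that exclusion in force. Neither alters any dose rule or threshold.

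If the separate statistical analysis plan does not already contain one, a table of holds, reductions and discontinuations by arm and trigger would be a useful addition, and can be built from data already on the CRF.

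The cost is one amended bullet, one sentence and a few more AE entries per site.

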#### **10.5.4. Grading of Adverse Events**

The severity of adverse events will be designated as mild, moderate, severe, life threatening, or fatal per NCI CTCAE version 5.0. If not specifically addressed in NCI CTCAE version 5.0, use [Table 3](#) below:

**Table 3: Adverse Event Severity**

Grade	Criteria 
Mild – Grade 1	Asymptomatic or mild symptoms; clinical or diagnostic observations only; intervention not indicated
Moderate – Grade 2	Minimal, local, or noninvasive intervention indicated; limiting age-appropriate instrumental ADL 
Severe – Grade 3	Severe or medically significant but not immediately life-threatening; hospitalization or prolongation of hospitalization indicated; disabling; limiting self-care ADL 
Life Threatening – Grade 4	Life-threatening consequences; urgent intervention indicated
Death – Grade 5	Death related to adverse event

 A semi-colon indicates 'or' within the description of the grade.

 Instrumental ADL refer to preparing meals, shopping for groceries or clothes, using the telephone, managing money, etc.

 Self-care ADL refer to bathing, dressing and undressing, feeding self, using the toilet, taking medications, and not bedridden.

#### **10.6. Relationship to Study Drug**

All AEs will be categorized by the investigator with respect to their relationship to GC4419/placebo. The relationship between GC4419/placebo and the AE may be considered related, possibly related, or unrelated. The criteria for each category are listed below:

- **Related:** It is likely that GC4419/placebo caused or contributed to the cause of the AE or laboratory abnormality, when the temporal sequence from the time of GC4419/placebo administration, the known consequences of the patient's clinical/state condition or study procedures, the effects of discontinuing or re-introducing GC4419/placebo on the AE, and other medically relevant factors are considered.

- **Possibly Related:** There is a reasonable possibility that the AE or laboratory abnormality was caused by GC4419/placebo, when the temporal sequence from the time of GC4419/placebo administration, the known consequences of the patient's clinical state/condition or study procedures, and other medically relevant factors are considered.
- **Unrelated:** The investigator has a high level of certainty that the patient's clinical state/condition, study procedures, or other medically relevant factors other than treatment with GC4419/placebo caused the AE or laboratory abnormality. This relationship category should only be used when a clear precipitating cause exists, and it is not reasonably possible that the event is caused by treatment with GC4419/placebo.

If the relationship between the AE/SAE and the investigational product is determined to be "possibly related" the event will be considered to be related to the investigational product for the purposes of expedited regulatory reporting.

## 10.7. Recording Adverse Events

All AEs must be recorded on the appropriate CRF regardless of the severity or relationship to GC4419/placebo. All AEs that meet the seriousness criteria should also be recorded on the SAE Report Form. All SAEs must be reported to the Sponsor or delegated organization within the timeline stated in [Section 10.5](#).

The recording of AEs will be based on data obtained from the following sources:

- Medical and surgical history
- Physical examinations including vital signs
- Clinical laboratory test results
- Subject verbal reports to the investigational staff and documented in the medical chart

All clinical events, including both observed (such as any reaction at sites of application) and volunteered problems, complaints, or symptoms, are to be recorded. The need to capture this information is not dependent upon whether the clinical event is associated with GC4419/placebo use. AEs resulting from concurrent illnesses, reactions to concurrent medications are also to be recorded.

The information to be recorded for AEs will include:

- The specific type of event in standard medical terminology – diagnosis if known, is preferred over symptoms
- Duration of the clinical event (start and stop dates)
- Severity (Grade 1, 2, 3, 4, or 5) of the clinical event
- Seriousness (SAE) criteria, if applicable
- Relationship of the AE to GC4419/placebo as defined in [Section 10.6](#)
- Management of GC4419/placebo administration and other action taken to alleviate the clinical events

- Clinical outcome of the AE

### **10.8. Follow-up of AEs and SAEs**

After the initial AE/SAE report, the investigator is required to proactively follow each patient and provide further information on the patient's condition. The investigator will ensure that follow-up includes any supplemental investigations as may be indicated to elucidate the nature and/or causality of the AE or SAE. This may include additional laboratory tests or investigations, or consultation with other health care professionals.

Non-serious AEs that have not resolved by the end of the prescribed Follow-up Period will be considered ongoing, and marked as such in the CRF. All SAEs will be followed until they resolve, or a new baseline is established, at which point the appropriate CRF page(s) or SAE Report Form(s) will be updated.

Routine collection of AEs will stop 30 days after the end of treatment.

As reasonably requested by the Sponsor, the investigator will perform or arrange for the conduct of supplemental measurements and/or evaluations to elucidate as fully as possible the nature and/or causality of the AE or SAE. If a patient dies during participation in the study or during a recognized follow-up period, Galera Therapeutics, Inc. will be provided with a copy of any post-mortem findings, including histopathology.

### **10.9. Post-Study Reporting Requirements**

Although such information may not be routinely sought or collected by Galera Therapeutics, Inc., SAEs that occur after the patient has completed a clinical study may be reported. Such cases will be evaluated for expedited reporting.

### **10.10. Pregnancy**

The risks of treatment with GC4419 during pregnancy have not been evaluated. Male subjects and female subjects of childbearing potential who engage in heterosexual intercourse should use a highly effective method of contraception starting at least on day prior to the first day of treatment and throughout the study and for 30 days (females) or 90 days (males) following the last dose of GC4419/placebo.

All females will be considered to be of childbearing potential unless they are postmenopausal (eg, amenorrheic for at least 12 consecutive months, in the appropriate age group, and without other known or suspected cause) or have been sterilized surgically (ie, bilateral tubal ligation, total hysterectomy, or bilateral oophorectomy, all with surgery at least 1 month before dosing). Subjects with a vasectomy or a vasectomized partner with confirmed azoospermia are eligible.

Highly effective methods of contraception include any of the following:

- total abstinence from heterosexual intercourse (per circumstances and lifestyle)
- an intrauterine device or intrauterine hormone-releasing system (IUS)

- a contraceptive implant
- an oral contraceptive at a stable dose of the same oral contraceptive product, begun at least 28 days before dosing and throughout the study and continued for 30 days after study drug discontinuation)

Pregnant and/or lactating females are excluded.

A subject who becomes pregnant must be withdrawn from the study.

Pregnancies or exposure to study drug through breastfeeding must be reported as soon as possible but no later than 24 hours from the date the investigator becomes aware of the event. The contact information for the reporting of pregnancies and exposure to study drug through breastfeeding is provided in the Investigator Study File. The outcome of the pregnancy must be reported as soon as possible but no later than 24 hours from the date the investigator becomes aware of the outcome.

#### **10.10.1. Time Period for Collecting Pregnancy Information**

As permitted by IRB/EC/REB policies, any pregnancy that occurs from the baseline visit up to 30 days after the last dose of GC4419/placebo should be reported using the appropriate form within 2 weeks of learning of the patient's pregnancy. The patient will be followed throughout the course of the pregnancy. Generally, follow-up will be no longer than six to eight weeks following the estimated delivery date. Any premature termination of the pregnancy should be reported. If a pregnancy is identified outside the 30 days after last dose, the investigator may report using clinical judgment.

#### **10.10.2. Action to be Taken if Pregnancy Occurs in a Female Partner of a Male Patient**

The investigator will attempt to collect pregnancy information on any female partner of a male study patient who becomes pregnant while participating in this study. The investigator will record pregnancy information on the appropriate form and submit it to Galera Therapeutics, Inc. within 2 weeks of learning of the partner's pregnancy. The partner will also be followed to determine the outcome of the pregnancy. Information on the status of the mother and child will be forwarded to Galera Therapeutics, Inc.. Generally, follow-up will be no longer than six to eight weeks following the estimated delivery date. Any premature termination of the pregnancy will be reported. If a pregnancy is identified outside the 30 days after end of treatment, the investigator may report using clinical judgment.

### **10.11. Regulatory Reporting of Adverse Events**

Galera Therapeutics, Inc. will have final determination of reportability and is responsible for notifying the relevant regulatory authorities of certain events. The investigator will report all SAEs that occur at his/her site to the IRB per the site's IRB regulations. AEs will be reported to regulatory authorities in compliance with 21 Code of Federal Regulations (CFR) 312.32, local and regional law and established guidance by the Sponsor or its designee. The format of the reports will be dictated by the local and regional requirements.

Investigators will also be notified of all unexpected, serious, drug-related events (7/15 Day Safety Reports) that occur during the clinical trial. Each site is responsible for notifying its IRB/IEC/REB of these additional SAEs in accordance with local or central IRB/IEC/REB procedures. Copies of each report will be kept in the investigator's files and adequate documentation will be provided to Galera Therapeutics, Inc. including documentation that the IRB/IEC/REB was notified of each safety report.

